6.1. Study Population

Individuals who do not meet the criteria for participation in this study (screen failure) may be re-screened. Individuals may be re-screened one time, if agreed upon by the investigator and the sponsor. The interval between screenings should be at least 1 week. When re-screening is performed, the individual must sign a new informed consent form (ICF) and will be assigned a new identification number. Repeating of laboratory tests during the screening period does not constitute re-screening; laboratory tests may not be repeated more than twice during the screening period in order to meet eligibility criteria.

Prospective approval of protocol deviations to recruitment and enrollment criteria, also known as protocol waivers or exemptions, are not permitted.

6.1.1. Inclusion Criteria

Patients may be included in the study if they meet all of the following criteria during screening prior to first dose of study drug.

(Note: If a specific cohort is not indicated for a criterion, the criterion applies to all patients.)

- [1] Must have histological or cytological evidence of a diagnosis of cancer that is not amenable to curative therapy.
- [2] Part B (all cohorts): Must have a type of malignancy that is being studied, as listed in the following:
 - [a] LY3022855 and durvalumab (MEDI4736) combination cohorts
 - [i] NSCLC that has relapsed or is refractory (definitions below) to immune checkpoint inhibitor therapy and has progressed through no more than 3 lines of therapy (one line must have been a platinum-containing regimen).
 - Relapsed: Following initial clinical benefit (that is, complete response [CR], partial response [PR], or stable disease [SD] on any scan), patients must have documented radiographic disease progression while receiving therapy with an immune checkpoint inhibitor.
 - Refractory: Patients must have documented radiographic disease progression ≤ 16 weeks after the start of treatment with an immune checkpoint inhibitor, with no evidence of clinical benefit (that is, CR, PR, or SD on any scan) while receiving therapy.

- a. Patients must not have a known activating mutation of the *EGFR* or *ALK* gene. If a site uses algorithmic testing that has eliminated the possibility of *EGFR* or *ALK* gene mutations, no specific testing for mutations in these genes is required.
- b. Patients could have received only one prior immune checkpoint therapy (anti-PD-1/PD-L1 or anti-CTLA-4, or a single regimen combining anti-PD-1/PD-L1 with an anti-CTLA-4).

[ii] Ovarian cancer (epithelial ovarian cancer, fallopian tube cancer, or primary peritoneal cancer) that has been treated with no more than 3 lines of therapy (with or without platinum).

- [3] Part A (all cohorts) and Part B (ovarian cancer cohort only): Must be willing to undergo pretreatment and on-treatment core needle or excisional tumor biopsies. For patient in NSCLC Part B cohort, if newly obtained samples cannot be obtained such as in cases of inaccessibility or patient safety concern, an archived tumor sample will be requested if not restricted by local regulations. The archived tumor sample must follow most recent systemic treatment. If no archived specimen since the most recent systemic treatment is available, and a new biopsy is not medically feasible, the patient should not be enrolled in the clinical trial.
- [4] [a] Part A (all cohorts): Have the presence of measurable and/or nonmeasurable disease as defined by the Response Evaluation Criteria in Solid Tumors (RECIST) 1.1 (Eisenhauer et al. 2009).
[b] Part B (both cohorts): Have the presence of measurable disease as defined by the RECIST 1.1 (Eisenhauer et al. 2009).
- [5] Are ≥ 18 years of age.
- [6] (Patient or legal representative) Have given written informed consent and any locally required authorization (for example, Health Insurance Portability and Accountability Act [HIPAA] in the United States or the European Union [EU] Data Privacy Directive) prior to performing any protocol-related procedures, including screening evaluations.
- [7] Have adequate normal organ and marrow function, including the following:

System	Laboratory Value
Hematologic	
ANC	$\geq 1.5 \times 10^9/\text{L}$ ($\geq 1500/\text{mm}^3$)
Platelet count	$\geq 100 \times 10^9/\text{L}$ ($\geq 100,000/\text{mm}^3$)
Hemoglobin	$\geq 9 \text{ g/dL}$ or $\geq 5.6 \text{ mmol/L}$ (red blood cell transfusions are not allowed within 7 days prior to screening hematology profile)
Renal	
Creatinine	$\leq 1.5 \times$ institutional ULN
OR	OR
Measured or calculated creatinine clearance ^a (see Attachment 6)	$\geq 60 \text{ mL/min}$
Hepatic	
Total bilirubin	$\leq 1.5 \times$ institutional ULN
AST and ALT	$\leq 2.5 \times$ institutional ULN OR $\leq 5 \times$ institutional ULN for patients with liver metastases
Coagulation	
INR or PT	INR $\leq 1.5 \times$ institutional ULN or PT ≤ 5 seconds above institutional ULN
PTT or aPTT	PTT or aPTT ≤ 5 seconds above institutional ULN
Thyroid	
TSH OR free T4	TSH OR free T4 within the normal limits.

Abbreviations: ALT = alanine aminotransferase; ANC = absolute neutrophil count; aPTT = activated partial thromboplastin time; AST = aspartate aminotransferase; GFR = glomerular filtration rate; INR = international normalized ratio; PT = prothrombin time; PTT = partial thromboplastin time; T4 = thyroxine; TSH = thyroid-stimulating hormone; ULN = upper limit of normal.

^a GFR should be estimated via the Chronic Kidney Disease Epidemiology Collaboration (CKD-EPI) creatinine equation (Levey et al. 2009).

[8] Have a performance status of ≤ 1 on the Eastern Cooperative Oncology Group (ECOG) scale (refer to [Attachment 5](#)).

[9] Have discontinued previous treatments for cancer and recovered from the acute effects of therapy.

At the discretion of the investigator, patients with hormone-refractory prostate cancer who are stable on gonadotropin-releasing hormone (GnRH) agonist therapy or maintenance prednisone, and patients with breast cancer who are stable on antiestrogen therapy (for example, an aromatase inhibitor) may have that treatment continued while they are enrolled.

[10] Are reliable and willing to make themselves available for the duration of the study and are willing and able to comply with the protocol for the duration of the study, including undergoing treatment, scheduled visits and examinations (including follow-up), and attempted pretreatment and on-treatment tumor biopsies (Part A – all cohorts and Part B – ovarian cancer cohort only).

[11] Have an estimated life expectancy, in the judgment of the investigator, of at least 12 weeks.

[12] Male patients:

[a] who are sterile (including vasectomy)

or

[b] who are not sterile and agree to use 2 acceptable methods of effective contraception* during the study, starting at screening, for at least 6 months following last dose of study drug(s); and agree not to donate sperm during the study and for at least 6 months following last dose of study drug

[13] Female patients:

[a] are women not of childbearing potential due to surgical sterilization (at least 6 weeks postsurgical bilateral oophorectomy with or without hysterectomy or tubal ligation) confirmed by medical history, or postmenopausal by history. Postmenopausal women include women with either:

[i] ≥ 60 years of age and spontaneous amenorrhea for at least 12 months, not induced by a medical condition such as anorexia nervosa and not taking medications during the amenorrhea that induced the amenorrhea (for example, oral contraceptives, hormones, GnRH, antiestrogens, selective estrogen receptor modulators [SERMs], or chemotherapy)

or

[ii] spontaneous amenorrhea for 6 to 12 months and a follicle-stimulating hormone (FSH) level greater than 40 mIU/mL

[b] are women of childbearing potential who test negative for pregnancy within 7 days prior to enrollment based on a urine or serum pregnancy test and agree to use 2 acceptable methods of effective contraception* during the study, starting at screening, and for 6 months following the last dose of the study drug(s) and also must not be breastfeeding.

* Acceptable methods of effective contraception include the following, where 2 methods must be used

- Barrier methods
 - Male condom plus spermicide
 - Cap plus spermicide
 - Diaphragm plus spermicide
- Intrauterine device methods
 - Copper T
 - Progesterone T (also considered to be a hormonal method)
 - Levonorgestrel-releasing intrauterine system (for example, Mirena®)
- Hormonal methods
 - Implants
 - Hormonal shot or injection
 - Combined pill
 - Minipill
 - Patch

Periodic abstinence, the rhythm method, and the withdrawal method are not acceptable methods of birth control.

6.1.2. Exclusion Criteria

Potential study patients may not be included in the study if any of the following apply during screening.

- [14] Have received treatment with an investigational product or nonapproved use of a drug or device (other than the study drug used in this study) within 28 days prior to the initial dose of study drug, or are concurrently enrolled in any other type of medical research judged not to be scientifically or medically compatible with this study.
- [15] Have been involved in the planning and/or conduct of the study (applies both to sponsor staff and/or to staff at the study site) or have an immediate family member (for example, spouse, parent/legal guardian, sibling, or child) who is investigational site or sponsor staff directly involved with this trial, unless prospective institutional review board (IRB) approval (by chair or designee) is obtained, allowing exception to this criterion for a specific patient.
- [16] Have previously been enrolled in the present study.
- [17] Have had any of the following anticancer therapies prior to enrollment:
 - [a] small molecule therapy or chemotherapy within 14 days.
 - [b] radiation therapy within 14 days.
 - [c] monoclonal antibody treatment within 28 days.
- [18] Are currently receiving or have had prior use of immunosuppressive medication within 28 days before the first dose of study drug, with the exception of intranasal and inhaled corticosteroids or systemic corticosteroids at physiological doses, which are not to exceed 10 mg/day of prednisone, or an equivalent corticosteroid.
- [19] Have had major surgery within 28 days prior to enrollment.
- [20] Have a serious preexisting medical condition, including, but not limited to, the following:
 - [a] Known human immunodeficiency virus (HIV) infection or acquired immunodeficiency syndrome (AIDS)-related illness (baseline screening required within 28 days prior to enrollment).
 - [b] History of immunodeficiency (primary and secondary).
 - [c] Active or prior documented autoimmune disease within the past 24 months. NOTE: Patients with vitiligo, Graves disease, or psoriasis not requiring systemic treatment (within the past 24 months) are not excluded.
 - [d] Active or prior documented inflammatory bowel disease (for example, Crohn's disease, ulcerative colitis).

- [e] Uncontrolled intercurrent illness, including, but not limited to, ongoing or active infection, symptomatic congestive heart failure, uncontrolled hypertension, unstable angina pectoris, cardiac arrhythmia, active peptic ulcer disease or gastritis, active bleeding diatheses including any patient known to have evidence of acute or chronic hepatitis B or hepatitis C.
- [f] History of allogeneic organ transplant.
- [g] Known history of tuberculosis.
- [h] Active non-infectious pneumonitis requiring treatment with steroids, or history of interstitial lung disease (ILD).
- [i] Active or uncontrolled clinically serious infection.
- [j] Known psychiatric or substance abuse disorders, or social situations that would either limit compliance with study requirements or compromise the ability of the patient to give written informed consent.

[21] Have symptomatic central nervous system (CNS) malignancy or metastasis (screening not required).

Patients with treated CNS metastases are eligible for this study if they are not currently receiving corticosteroids greater than 10 mg per day of prednisone or equivalent, and their disease is asymptomatic and radiographically stable for at least 60 days.

[22] Have a second primary malignancy that, in the judgment of the investigator and sponsor, may affect the interpretation of results.

[23] Have mean QT interval corrected for heart rate (QTc) ≥ 470 milliseconds calculated from one baseline electrocardiogram (ECG) using Fridericia's Correction Formula (QTcF) and confirmed with 2 additional baseline ECGs.

[24] Have known hypersensitivity to LY3022855, durvalumab, or tremelimumab, or to any combination or excipient.

[25] Have received live attenuated vaccination within 30 days prior to study entry.

[26] Have any condition that, in the opinion of the investigator, would interfere with evaluation of study treatment or interpretation of patient safety or study results.

[27] Have known muscle damage due to a primary, traumatic, or other muscle disease or a creatine kinase greater than normal limits.

[28] Have had any prior Grade ≥ 3 irAE† while receiving any previous immunotherapy agent, have any unresolved irAE Grade > 1 , or any irAE that led to the permanent discontinuation of prior immunotherapy.

- [29] Have experienced a Grade ≥ 3 AE or a neurologic or ocular AE of any grade while receiving prior immunotherapy. Patients with an endocrine AE Grade ≤ 2 are permitted to enroll if they are stably maintained on appropriate replacement therapy and are asymptomatic.
- [30] Have required the use of additional immunosuppression other than corticosteroids for the management of an AE, have experienced recurrence of an AE if re-challenged, and currently require a maintenance dose of >10 mg prednisone or equivalent per day.
- [31] Have left ventricular ejection fraction (LVEF) $<50\%$.
- [32] Have known *ROS1* mutation in NSCLC (baseline screening not required).

† Immune-related AEs: pneumonitis or ILD; diarrhea or enterocolitis; hepatitis (elevated liver function test); nephritis or renal dysfunction (elevated serum creatinine); rash (excluding bullous skin formations); endocrinopathy (for example, hyperthyroidism, hypothyroidism, hypopituitarism, adrenal insufficiency); immune-mediated neurotoxicity (including but not limited to limbic encephalitis, autonomic neuropathy, excluding myasthenia gravis and Guillain-Barre); immune-mediated peripheral neuromotor syndromes, such as Guillain-Barre and myasthenia gravis.

6.1.3. **Lifestyle Restrictions**

Patients should not donate blood while participating in this study until after 4 to 5 times the half-life of study treatment(s) (that is, 6 months after the last dose).

6.2. **Summary of Study Design**

Study I5F-MC-JSCC is a multicenter, nonrandomized, open-label, dose-escalation (Part A), followed by dose-expansion (Part B) Phase 1a/1b study of LY3022855 in combination with durvalumab or tremelimumab (Part A) or durvalumab only (Part B), in patients with advanced solid malignancies. A cycle is defined as 28 days (4 weeks). Eligible patients will receive treatment as follows:

- LY3022855 (once weekly [QW] OR once on Days 1, 8, and 15 of each cycle OR once every 2 weeks [Q2W]), in combination with:
 - durvalumab Q2W (Parts A and B)
OR
 - tremelimumab once every 4 weeks (Q4W); after 6 doses, tremelimumab once every 12 weeks (Q12W) until discontinuation (Part A only)

The study will be conducted in 2 parts:

[figure not shown]
- Part A – Phase 1a, dose escalation
- Part B – Phase 1b, disease-specific expansion

The following description applies to each combination therapy.

During Part A, patients will be enrolled in a 3+3 design. In the LY3022855-plus-durvalumab regimen, LY3022855 will be administered at increasing dose levels, as tolerated; durvalumab will be administered at a fixed dose. In the LY3022855-plus-tremelimumab regimen, both LY3022855 and tremelimumab will be administered at increasing dose levels, as tolerated. In the event DLTs prevent further dose escalation (LY3022855 [in both combinations] and tremelimumab only), additional dosages between the highest dose tested and the previously identified safe dosage may be explored after further discussion among the investigators, sponsor, and collaborator. Once a maximum tolerated dose (MTD) has been identified for the LY3022855-plus-durvalumab combination, enrollment to Part B (2 disease-specific expansion cohorts of 20 patients per cohort) will begin. The NSCLC cohort will consist of a minimum of 10 patients with disease refractory to checkpoint therapy and a minimum of 6 patients with disease relapsed on prior checkpoint therapy. Patients in Part B will be treated at the MTD for LY3022855-plus-durvalumab combination. Upon completion of Part B, which is intended to confirm tolerability of a combination dose, the RP2D will be declared/defined.

All patients enrolled to all cohorts of Part A or to the ovarian cancer cohort (only) of Part B will undergo mandatory attempted pretreatment and on-treatment (6-8 weeks after starting study treatment) tumor core needle or excisional biopsies.

[Figure JSCC.7](#) presents the overall study design. [Figure JSCC.8](#) presents the schema for an individual patient with regard to timing of tumor tissue biopsies.

Abbreviations: MTD = maximum tolerated dose; NSCLC = non-small cell lung cancer; pts = patients.

Note for Part A: Only LY3022855 (in both combinations) and tremelimumab, but not durvalumab, are dose escalated.

Figure JSCC.7.

JSCC study design.

[figure not shown]

Figure JSCC.8. Schema for an individual patient with regard to timing of tumor tissue biopsies.

To characterize the safety profile and tolerability and to define the RP2D of the combinations of LY3022855 with durvalumab or tremelimumab, an adequate sample size is required. The actual sample size in Part A depends on the incidence of DLTs and is estimated to be up to approximately 78 patients; refer to Section 10.1 for additional details.

In Part A, after all patients who are deemed evaluable for the assessment of dose levels complete the DLT-evaluation period or the MTD is determined, an interim safety and PK analysis may be conducted for each combination for planning next studies. After completion of enrollment to Part B, if it is deemed that enough data are obtained to assess the primary and secondary objectives, a clinical study report may be written before the last patient visit for the study.

The planned duration of treatment is not fixed; patients will remain on study until they fulfill one of the criteria for study discontinuation (Section 6.3).

Refer to [Attachment 1](#) for the Study Schedule.

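### Exclusion criterion 30 joins its three conditions with *and*, so as written it excludes nobody whom criterion 18 does not already exclude

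*Protocol*

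**What the plan says.** The list in Protocol section 6.1.2 opens with its governing rule: "Potential study patients may not be included in the study if any of the following apply during screening". Meeting any one numbered criterion is therefore enough to exclude a patient.

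Criterion 30 is a single sentence. It concerns patients who have needed immunosuppression beyond corticosteroids to manage an AE, "have experienced recurrence of an AE if re-challenged, and currently require a maintenance dose of" a steroid above a threshold. The closing clause in full is "currently require a maintenance dose of >10 mg prednisone or equivalent per day".

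Criterion 18 excludes patients who "Are currently receiving or have had prior use of immunosuppressive medication within 28 days before the first dose of study drug". It exempts intranasal and inhaled corticosteroids and "systemic corticosteroids at physiological doses, which are not to exceed 10 mg/day of prednisone, or an equivalent corticosteroid".

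Two neighbouring criteria also screen on prior immunotherapy, and both join their conditions with *or*:

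- Criterion 28 excludes a prior immune-related AE (irAE) of Grade 3 or above, an unresolved irAE above Grade 1, or "any irAE that led to the permanent discontinuation of prior immunotherapy".
- Criterion 29 excludes an AE of Grade 3 or above, or a neurologic or ocular AE of any grade, on prior immunotherapy. It makes an allowance for stable, replaced endocrine events up to Grade 2.

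Nothing else in the documents restates or corrects criterion 30. It is not among the sections revised in the amendment (c) summary, and the SAP does not list eligibility criteria.

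**The concern.** Criterion 30 names two kinds of history that look relevant when a patient is about to receive another checkpoint inhibitor: an event that needed more than steroids, and an event that came back on re-challenge. Tied by *and* to a current steroid dose that is already disqualifying, neither history affects eligibility.

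This matters most in the Part B lung cancer cohort. Inclusion criterion 2 requires every patient in it to have relapsed on, or been refractory to, a checkpoint inhibitor, and each then receives durvalumab with LY3022855. Section 5.3 warns that irAEs may be more frequent with the combinations than with the single agents.

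In Part A, section 7.2.2.2 stops escalation when 2 or more of at most 6 patients in a cohort have a dose-limiting toxicity. The history of a single patient could therefore count there, although the documents give no basis for saying how often.

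Section 6.1 forbids eligibility waivers, so sites must apply the wording as it stands. A site that reads criterion 30 as three separate exclusions and a site that reads it literally would enrol different patients.

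**Working it through.** No sample size, error rate or stated figure is involved. The check is one of logic.

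**Inputs, all from section 6.1.2**

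- A: needed non-corticosteroid immunosuppression for an AE (criterion 30)
- B: the AE recurred on re-challenge (criterion 30)
- C: currently needs more than 10 mg/day prednisone or equivalent (criterion 30)
- S: took a non-steroid immunosuppressant within 28 days before the first dose (criterion 18)
- G: excluded by criterion 28 or 29

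**Rules**

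- Criterion 18 = C or S. Its exemption for systemic steroids stops at 10 mg/day, so C alone triggers it.
- Criterion 30 as written = A and B and C.
- Criterion 30 with each condition sufficient = A or B or C.

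Five yes/no facts give 2^5 = 32 logical profiles.

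**As written**

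- A, B and C must all be true, which leaves S and G free: 2 × 2 = 4 profiles.
- C is true in all 4, so criterion 18 excludes all 4.
- Profiles excluded by 30 but not by 18: **0**.

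In words, (A and B and C) implies C, and C implies exclusion under 18. Criterion 30 lies wholly inside criterion 18.

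**If each condition alone excluded**

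- Only A = B = C = no escapes criterion 30, which is 2 × 2 = 4 profiles. It would cover 32 − 4 = 28.
- Escaping criterion 18 requires C = no and S = no, leaving A, B and G free: 2 × 2 × 2 = 8 profiles. Removing the 2 with A = B = no leaves **6** that criterion 30 catches and 18 does not.
- Requiring also that 28 and 29 do not apply (G = no) leaves **3**: A only, B only, and A with B, each with current steroid at or below 10 mg/day.

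These are counts of logical profiles. They are not patient frequencies.

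**Who falls in those 3 profiles**

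Setting criteria 18, 20, 26, 28 and 29 side by side, the earlier AE must meet all of the following:

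- It was Grade 2 or lower, and neither neurologic nor ocular.
- If it was an irAE, it has resolved to Grade 1 or lower and did not permanently end prior immunotherapy.
- It is not caught by the medical conditions in criterion 20 or by investigator judgement under criterion 26.
- It either needed a non-steroid immunosuppressant last used more than 28 days before dosing, or recurred on re-challenge.

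Condition A can arise at Grade 2. The protocol's own Attachment 7 moves Grade 2 colitis that does not respond to steroids to infliximab, and Grade 2 hepatitis to mycophenolate.

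**The case against.** The strongest reply is that other screens already cover most of the ground. Criterion 28 catches any unresolved irAE above Grade 1, even if therapy continued, and criterion 29 catches low-grade neurologic and ocular events. Criterion 20 covers interstitial lung disease, inflammatory bowel disease and recent autoimmune disease. Criterion 26 gives the investigator discretion, and inclusion criterion 9 requires recovery from the acute effects of earlier therapy. All of this stands, and it makes the affected group narrow. None of it gives conditions A and B any effect, and criterion 26 is a judgement that can vary by site.

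A second reply is that the lung cancer cohort leaves little room for such histories. Only one prior checkpoint therapy is allowed. At least 10 of the approximately 20 patients must be refractory, with progression within 16 weeks of starting it. That is a fair reason to expect few cases, possibly none.

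A third is that Attachment 7 itself allows re-dosing after Grade 2 colitis treated with infliximab, once the event is Grade 1 or lower and the steroid taper is complete. For condition A, the protocol may therefore not regard such patients as unsuitable. This bears on which rule the sponsor wants, and it is a reason not to assume the answer.

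A fourth is that overlap between criteria does not prove an error. A Grade 3 irAE, for example, is excluded by both 28 and 29. Here, though, a whole criterion is absorbed by another and two of its three conditions do nothing.

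Criterion 18 speaks of receiving steroids and 30 of requiring them. A patient who needs more than 10 mg/day but is not taking it is a theoretical exception only, and would not restore the effect of A or B as separate screens.

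**Conclusion.** The redundancy is certain on the text, apart from that edge case: as written, criterion 30 adds zero exclusions to criterion 18. That the conditions were meant to stand alone is an inference from two facts: A and B are otherwise idle, and 28 and 29 use *or*. No rationale section explains criterion 30.

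A reader might go further in two ways that the documents do not support:

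- **That an intended safety screen has been shown to have failed.** Intent is not stated, and the documents do not give the risk of severe recurrence in these patients.
- **That all 20 lung cancer patients are exposed to a gap.** The approximately 20 are only the pool with guaranteed prior checkpoint exposure, to which any pretreated Part A patients are added. Those actually affected are the narrow group set out above. Their frequency is not given and may be small.

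No analysis or sample size depends on this point. It is still worth correcting: an eligibility rule in a Phase 1 checkpoint-inhibitor combination does not work as worded, and settling the wording can change who is enrolled.

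**What to change.** Reconcile criterion 30 with criteria 18, 28 and 29 by protocol amendment, in one of two ways:

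- Reword criterion 30 so that it is explicit whether each of its three conditions excludes on its own.
- Delete it, if criterion 18 is all that was meant.

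Which rule is clinically right is for the sponsor to decide and state. Either change takes about a line of text. If each condition is made sufficient, there may be a few more screen failures. Deletion changes nothing about who is eligible under the literal reading, but it removes the room for sites to read the criterion differently.
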